5.5.2 Intervention Administration

The 3RP will be administered virtually via Partners Telehealth videoconferencing software by the PI or by a member of the study team who has doctoral-level training in clinical psychology and is experienced in conducting the 3RP (e.g. clinical psychologists, fellows, post-docs). The 3RP consists of eight, 1.5 hour weekly RR-training group sessions conducted over the course of approximately 8 weeks, and there will be approximately 6 patients per group. The topics addressed in the eight 3RP sessions are listed in Appendix 8.9. Prior to the first 3RP session, participants may have the option to complete a brief, approximately 10-minute

initial visit with a 3RP provider over the phone, via Partners Telehealth videoconferencing software, or in-person at MGH, in accordance with patient and provider availability. The purpose of the initial session is to identify participants' goals for the program. Additionally, as described in protocol section 4.2, in order to facilitate proficiency with the Telemedicine software, participants will test the software with a study staff member during a brief test call prior to the start of the intervention.

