6.0 STATISTICAL ANALYSIS

This study will assess the feasibility and acceptability of the 3RP among approximately 55 lymphoma survivors who are less than 2 years post-treatment using descriptive analyses.

6.1 Primary and secondary endpoints.

The primary study endpoints are the feasibility and acceptability of the program for lymphoma survivors who are within 2 years post-treatment completion. These will be detailed further below in the data analysis section.

6.2 Sample Size and Power Calculations.

This phase of the study is designed as an open pilot and thus is exploratory. Though our analyses are not powered to detect an effect, the aim of this pilot is to adapt and test the feasibility and acceptability of a mind-body based stress management program. Our emphasis on establishing feasibility and acceptability is consistent with best practices in treatment development.^{27,59} We consider a 75% session completion rate as a threshold for establishing intervention feasibility. With a sample size of 30 for the 3RP-Lymphoma, we would have 90% power to demonstrate a mean participation rate 5.5% higher than the threshold with a one-sided significance level of 0.05, assuming the SD of participation rate is 10%. Therefore, we believe our sample size of 55 will be sufficient to answer our questions about feasibility and acceptability.

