Exploratory Aim c) We will examine the preliminary effects of the intervention on psychosocial measures of fatigue, mindfulness, depressed mood, anxiety, and stress.

Preliminary outcome data may be used to inform future assessment instruments and methods. We may also conduct exploratory hypothesis testing to examine preliminary changes in our proposed intervention targets (changes in fatigue, mindfulness, depressed mood, anxiety, stress). A priori statistical tests of intervention-related changes will be planned for a future efficacy trial of this intervention. We will compare baseline demographic and clinical characteristics between completers and non-completers using chi square tests and t-tests. Paired samples T-tests will be used to examine pre and post-intervention differences (T2 vs T1) at $p < .05$ for each of our exploratory outcomes (e.g. CAMS-R). We will also assess the sustained effects of treatment with a repeated measures ANOVA analysis, including the 3 survey time points. This analysis will allow us to assess if there is a trend towards maintenance of treatment effects but is not powered to detect significant differences.

Exit interviews (Appendix 8.7) will be audio-recorded and transcribed; NVIVO software will be utilized in the thematic analysis, which will be led by [name] and the study RA under the mentorship of [name], who directs the Qualitative Research Core at MGH. [name] and the study RA will meet on a weekly basis to discuss the coding framework, categories, and coding plan. To ensure coding reliability, coding discrepancies will be resolved through discussion and comparison of raw data. Coding will continue until a high level of reliability ($\text{Kappa} = > 0.80$) is established.

6.9 Handing of missing data in the analysis.

This phase of the study is intended to test the feasibility and acceptability of the stress management program. We will explore differences between study completers and non-completers on patient demographic and other relevant variables to inform the next phase of this trial. We will assess whether the mechanism of missing data is missing at random. We will perform sensitivity analysis using: 1) a completer analysis limited to those who have complete data and 2) multiple imputations for missing data.⁶⁰ To address missing data at follow-up, participants who are no longer interested in participating in the 3RP sessions will still be given the option to complete follow-up assessments.

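### The 90% power in section 6.2 assumes no correlation within the treatment groups of about 6, and the exploratory pre-post tests in section 6.8 ignore the grouping

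*Combined protocol and SAP*

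**What the plan says.** Section 5.5.2 describes eight weekly sessions by videoconference and says that "there will be approximately 6 patients per group". The leader is the principal investigator or another doctoral-level team member.

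Section 6.2 sets the benchmark: "We consider a 75% session completion rate as a threshold for establishing intervention feasibility". For 30 participants it then states that "we would have 90% power to demonstrate a mean participation rate 5.5% higher than the threshold". The other inputs are one-sided alpha 0.05 and an SD of 10%. It gives no ICC, design effect or number of groups, and ends: "Therefore, we believe our sample size of 55 will be sufficient to answer our questions about feasibility and acceptability". Section 5.1 allows up to 55 enrolments so that about 40 people take part in the programme.

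Section 6.8 summarises feasibility and acceptability descriptively. For the exploratory psychosocial outcomes it says: "Paired samples T-tests will be used to examine pre and post-intervention differences", at p < .05 for each outcome, and adds a repeated measures ANOVA over the three survey times. Neither has a term for treatment group, and section 6.9 on missing data adds none.

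**The concern.** People in one group share a time slot, the same sessions and one another. Contact with other survivors is part of the rationale: in section 5.3 the Phase 1 participants said that a group programme with other survivors would help. Some correlation of attendance, and of change in outcome, within groups is therefore foreseeable, although the documents do not quantify it.

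Two things depend on it. The first is the 90% in section 6.2, which is the only quantitative support for the sample size. The second is the p < .05 rule in section 6.8. A test that treats people in a group as independent uses too small a standard error when the ICC is positive, and so rejects too often. Section 6.9 says that results will inform the next phase, so understated standard errors and an unreported ICC would carry forward into its design.

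**Working it through.** **Inputs.** From section 6.2: n = 30, difference 5.5 percentage points, SD 10 points, one-sided alpha 0.05. From section 5.5.2: group size m = 6. From section 5.1: about 40 starters. From sections 5.1 and 6.2: 55 accrued. Assumed, because the documents give none: ICC of 0.05 and 0.10. The ICC for attendance and the ICC for outcome change are separate quantities; the same two values are used for both as illustration.

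**Step 1: reproduce the stated 90%.** For a one-sample t-test on independent people, the noncentrality is 5.5 / (10/√30) = 3.01 with 29 degrees of freedom. Power is 90.3% (91.4% by the normal approximation), so the plan's figure reproduces. It does not reproduce two-sided (82.9%), or if 5.5% is read as a relative increase of 0.055 × 75 = 4.125 points (71.3%). The figure is thus a calculation for 30 independent participants.

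**Step 2: allow for groups.** Design effect = 1 + (m − 1) × ICC:

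- ICC 0.05: 1 + 5 × 0.05 = 1.25
- ICC 0.10: 1 + 5 × 0.10 = 1.50

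Effective n = n / design effect. The noncentrality becomes 5.5 / (10/√effective n).

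| n | ICC | Effective n | Power, df = n − 1 | Power, df = n/6 − 1 |
|---|---|---|---|---|
| 30 | 0 | 30.0 | 90.3% | 79.4% |
| 30 | 0.05 | 24.0 | 83.8% | 71.5% |
| 30 | 0.10 | 20.0 | 77.5% | 64.8% |
| 40 | 0 | 40.0 | 96.2% | 91.7% |
| 40 | 0.05 | 32.0 | 92.1% | 85.8% |
| 40 | 0.10 | 26.7 | 87.4% | 79.9% |
| 55 | 0 | 55.0 | 99.1% | 98.1% |
| 55 | 0.05 | 44.0 | 97.5% | 95.4% |
| 55 | 0.10 | 36.7 | 95.0% | 91.8% |

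The last column shows a test with group-level degrees of freedom. Part of its loss comes from the few degrees of freedom and not from correlation: at n = 30 and ICC 0, going from 29 to 4 degrees of freedom alone costs about 11 points (90.3% to 79.4%).

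**Step 3: how much correlation the surplus over 30 absorbs.** By the normal approximation, 90% power needs an effective n of ((1.645 + 1.282) × 10 / 5.5)² = 28.3. Solving n / (1 + 5 × ICC) = 28.3 gives an ICC of about 0.01 at n = 30, 0.08 at n = 40 and 0.19 at n = 55. These limits do not include the cost of group-level degrees of freedom.

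**Step 4: error rate of a paired test that ignores groups.** Its standard error is too small by √1.25 = 1.12 at ICC 0.05 and √1.50 = 1.22 at ICC 0.10. A nominal two-sided 5% test then has a true error of about 2 × [1 − Φ(1.96/1.12)] = 8.0% and 2 × [1 − Φ(1.96/1.22)] = 11%. Simulation with groups of 6 agrees (about 8% and 11%) and gives nearly the same with five groups as with seven. More groups do not cure it, because the design effect depends on group size and ICC and not on the number of groups. A t-test on group means stays at about 5%.

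**The case against.** The case against is substantial, and much of it stands.

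- *The tests carry little weight.* Section 6.2 says that the analyses are not powered to detect an effect, and section 6.8 calls the outcome tests exploratory and leaves a priori tests to a future trial. This stands and limits the importance of the point. But section 6.8 still names p < .05 for each outcome, and that rule is what grouping distorts.
- *Attendance is not formally tested.* The one-sided test against 75% appears only in the sample size rationale; section 6.8 treats attendance descriptively. This stands. The attendance part of the point is that the 90% is conditional, not that a planned attendance test is invalid.
- *More than 30 people are planned.* This stands for power, as step 3 shows. It does not repair the error rate in step 4.
- *The ICC is unknown, and one leader running every group would add no variation between groups.* Also fair. Shared sessions and peers remain as sources of correlation, but the size can only be shown as a range.

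A reader might go further and infer that the study is underpowered, that its confidence intervals are too narrow, or that every planned comparison is affected. The documents do not support these readings. About 40 to 55 people are planned, not 30. No confidence intervals are planned. The comparison of completers with non-completers uses baseline characteristics, which group sessions cannot have influenced.

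**Conclusion.** The point holds as a conditional one. The 90% in section 6.2 is correct for 30 independent people and is too high at that n for any positive ICC: about 84% at 0.05 and 78% at 0.10. At about 40 starters the same test has about 92% and 87% (86% and 80% with group-level degrees of freedom), and at 55 about 97% and 95%. The sample may well be adequate, but section 6.2 does not show this.

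The paired t-tests in section 6.8, if run at a nominal two-sided 5%, would have a true error of about 8% and 11% at those ICCs. The repeated measures ANOVA shares the omission; its error rate was not calculated. The descriptive feasibility estimates do not change.

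All sizes rest on assumed ICCs, equal groups of 6, and the plan's own SD and difference. This is a worthwhile correction to an exploratory pilot and does not challenge its primary conclusions.

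**What to change.** In section 6.2, say that the 90% assumes no within-group correlation, and give the power at ICC 0.05 and 0.10 for the roughly 40 people expected to start sessions.

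In section 6.8, test pre-post changes with a mixed model that has a random intercept for group and small-sample degrees of freedom, or with a t-test on group means. Allow for group likewise in the three-time-point analysis. If mean attendance is to be tested against 75%, treat it the same way. Report the ICC with its uncertainty for the next trial.

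The cost is SAP wording and a restated power figure; no extra participants, visits or data are needed, since group membership is known from delivery. The downside is less favourable p-values and an imprecise group variance, because 40 / 6 gives only about 7 groups. The reported ICC will be equally imprecise.

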5.5.3 Special Concerns

Some participants may feel uncomfortable sending us a hair sample; participants will not be required to participate in the hair sample collection if they feel uncomfortable or are otherwise unable to provide a hair sample. Participants can still remain in the study if they do not wish to complete a hair cortisol sample. Additionally, some subjects may not wish to participate in the weekly 3RP Session Evaluation Surveys or a qualitative exit interview for the study; these components of the study will be considered optional.

5.5.4 Compensation.

Subjects will receive \$10 in remuneration for completion of the baseline survey, and \$15 in remuneration for completion of the post-3RP and follow-up surveys (up to \$45 total). Participants will receive \$15 in remuneration for completion of the baseline and follow-up hair sample(s) (up to \$30 total). As required for compliance with Partners Healthcare remuneration policy, we will collect participants' contact information (see Remuneration Form in Appendix 8.13).

5.6 Adverse Reactions and Their Management

5.6.1 Reported Adverse or Unanticipated Events. We do not anticipate any adverse events as a result of study participation. The RA, in collaboration and discussion with the PI, will report to the Institutional Review Board (IRB) in a timely manner any discovery of an unanticipated or adverse event. An adverse event will be reportable to the IRB if it meets the following criteria: a) affects patient safety; b) affects patient risk-benefit assessment to participating in the study; and c) affects data integrity. Study staff will report adverse events to the IRB as soon as they are discovered and discussed with the PI or designee (within 24 hours). The PI will be responsible for cataloguing and tallying adverse events, and she will report these events to the DF/HCC IRB as well as review the report with the mentors of the proposed study. Study staff will also be required to undergo NIH training in the conduct of research with human subjects prior to engaging in any research activities.

5.6.2 Anticipated Reactions. We do not anticipate that participants will experience any serious adverse reactions. Some participants may experience feelings of distress, sadness or emotional/physical fatigue when discussing stress and/or cancer-related topics. The PI is a licensed clinical psychologist with advanced training in clinical interviewing and assessment. Participants will be instructed to skip or decline answering any survey or interview questions that they find upsetting or uncomfortable. We also aim to reduce participant burden by allowing for the option to complete interviews via the phone or Partner's Telehealth videoconferencing software.

While this study does not target participants with depression or anxiety, it is possible that some will experience these conditions and related symptoms. The study PI is a licensed psychologist, who will evaluate and meet with any patient experiencing distress related to study participation, to determine if the patient requires further intervention.

As described in section 4.2 of the protocol, although we will instruct participants to maintain the confidentiality of the group by not discussing anything that goes on in the group with others, we cannot guarantee that group members will not share the content of the group with others. Extra attention will be taken during the informed consent process to explain this risk to participants. In addition, participants will be advised to wear headphones and sit in a quiet place to protect their own, and other group members', privacy.

5.6.3 Reaction Management. If, during the course of the study, study participants become distressed, the PI will be available to discuss the patient's concerns. If any aspects of the study make the participant very upset, appropriate follow-up action will be taken by the PI who will assess for safety and make appropriate referrals for treatment (e.g., MGH oncology social services). [name], a clinical psychologist with extensive experience working with cancer patients, will consult with the study team on complicated situations involving psychological distress at team meetings or as needed.

6.0 STATISTICAL ANALYSIS

This study will assess the feasibility and acceptability of the 3RP among approximately 55 lymphoma survivors who are less than 2 years post-treatment using descriptive analyses.

6.1 Primary and secondary endpoints.

The primary study endpoints are the feasibility and acceptability of the program for lymphoma survivors who are within 2 years post-treatment completion. These will be detailed further below in the data analysis section.

6.2 Sample Size and Power Calculations.

This phase of the study is designed as an open pilot and thus is exploratory. Though our analyses are not powered to detect an effect, the aim of this pilot is to adapt and test the feasibility and acceptability of a mind-body based stress management program. Our emphasis on establishing feasibility and acceptability is consistent with best practices in treatment development.^{27,59} We consider a 75% session completion rate as a threshold for establishing intervention feasibility. With a sample size of 30 for the 3RP-Lymphoma, we would have 90% power to demonstrate a mean participation rate 5.5% higher than the threshold with a one-sided significance level of 0.05, assuming the SD of participation rate is 10%. Therefore, we believe our sample size of 55 will be sufficient to answer our questions about feasibility and acceptability.

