5.0 STUDY DESIGN AND METHODS

5.1 Design / Study Type

This is a single-arm feasibility trial to examine the feasibility and acceptability of the 3RP among approximately 55 lymphoma survivors who are less than 2 years post-treatment. Participants who sign informed consent but who are found to be ineligible during the brief test call; those who do not complete any study

measures; and those who withdraw or are removed from the study prior to participating in any 3RP group sessions will not be counted towards the accrual goal of 55 participants. As such, up to 55 participants may be enrolled in the study in order to allow approximately 40 patients to participate in the 3RP. We will keep a detailed log of these instances, as this will inform the feasibility of the study. Participants do not need to complete every study measure to be counted towards the 55 accrual goal (participants who only complete some measures/3RP sessions will still be counted towards the accrual goal); however, patients who do not complete any of the study measures or who do not participate in any 3RP sessions will not be counted towards this goal.

All patients, regardless of whether they are counted towards the 55 accrual goal, will be included in the feasibility assessment. We plan to examine the proportion of patients who are eligible and the proportion who are found to be ineligible due to age, language, inability to use the videoconferencing software, oncologist refusal, and medically or psychiatrically unable to participate. Out of those who are eligible, we will examine the proportion of enrollments, refusals, lost-to-follow up, withdraws, and study completers. We will examine reasons for and rates of ineligibility, as these will inform the feasibility of the study and of delivering the program virtually. We will also examine the characteristics of non-completers and the reasons for non-completion.

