The 3RP will thus be delivered in weekly sessions over the course of approximately 8 weeks, for a total of 8 sessions which are approximately 90 minutes each. Modeled after the central tenets of the 3RP,¹ each session includes repetition of core components, which include: 1) 10-point analogue scales of stress, distress, and coping (resembles distress thermometer), 2) weekly goal check-ins, 3) RR-practice, and 4) mini relaxation practice. Participants will learn a new RR strategy at each session that will be based on identified mind-body interests, maximizing the likelihood of finding a technique that is helpful for them. Throughout treatment, participants will be encouraged to practice RR strategies at home for at least 10-20 minutes each day, and they will be asked to document the frequency and duration of practice in weekly practice logs (Appendix 8.3) to record RR adherence. Participants will receive the 3RP patient manual, which describes the content of the 3RP sessions, and RR-based guided meditation CDs or audio files to help them elicit the RR at home each day. The CDs that guide the subject through the procedures have been used in other clinical research studies and clinical practice. It introduces a relaxation sequence to help participants elicit the RR, including some of the key elements such as breath awareness, body scan and use of a focus word, while instructing the participant to passively ignore intrusive thoughts. Additional treatment components based on the 3RP model (Figure 1) and identified qualitative interview themes include coping logs that provide examples drawn from common transitional challenges identified by survivors in the Phase 1 interviews, which will facilitate discussion and practice of restructuring and positive reframing techniques. Lastly, social and educational topics identified in Phase 1 will be interwoven throughout the program and used to guide survivors in applying learned skills (e.g., identifying types of social support needed and developing strategies to facilitate outreach and connection). At the end of each session, the interventionist will complete a process form indicating the length, location and content of the session. We will also collect total number and timing of sessions per participant. The topics addressed in each of the eight 3RP sessions are described in Appendix 8.9.

5.4 Data Collection and Storage.

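### Section 6.2's 90% power at n=30 rests on an unsourced SD of 10 points that fits poorly with a rate out of 8 sessions, and 6.8 has no bound or test of mean participation against the 75% threshold

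*Combined protocol and SAP*

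**What the plan says.** Section 6.2 sets the criterion: "We consider a 75% session completion rate as a threshold for establishing intervention feasibility". It then states 90% power, with 30 participants, to demonstrate a mean participation rate 5.5% above that threshold, at a "one-sided significance level of 0.05, assuming the SD of participation rate is 10" percent. No source is given for the SD; the citations in that paragraph support the emphasis on feasibility. The paragraph ends: "Therefore, we believe our sample size of 55 will be sufficient to answer our questions about feasibility and acceptability".

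Section 5.3 fixes the unit of measurement, "for a total of 8 sessions which are approximately 90 minutes each", and provides the data: "We will also collect total number and timing of sessions per participant".

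Section 5.1 gives two accounts of the 55. People "who do not participate in any 3RP sessions will not be counted towards this goal", which makes 55 a number of attenders. Yet "up to 55 participants may be enrolled in the study in order to allow approximately 40 patients to participate in the 3RP", which makes 55 a number enrolled and about 40 the number of attenders.

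Section 6.8, Aim a, is descriptive. It lists means, frequencies and ranges, attendance at each session, and a completer label at 6 of 8 sessions. It gives no test or confidence bound for mean participation against 75%, and no denominator for that mean.

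**The concern.** The SD largely determines the answer in 6.2, and it is not a free choice. Each person's rate is a count out of 8 divided by 8, so its spread is tied to the mean and to how sessions are attended. At the mean of 80.5% that the calculation is meant to detect, 10 points is less than independent, equally attended sessions would produce. The usual departures go the other way: some people attend more reliably than others, and some stop. Section 6.9 itself provides for participants who lose interest in the sessions.

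Feasibility is a primary endpoint, 75% session completion is the only threshold the plan gives for establishing it, and 6.2 is the only quantitative justification of the sample size. If the SD is larger than 10, a programme modestly above 75% is less likely to be shown to be so than 6.2 says. Because 6.8 specifies no bound, a reader of the results would also have no pre-stated way to judge whether an observed mean in the high 70s clears the threshold.

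**Working it through.** **Inputs.** From 6.2: threshold 75%, excess 5.5 points (mean 80.5%), one-sided alpha 0.05, SD 10 points, n=30, planned size 55. From 5.1: about 40 taking part. From 5.3: 8 sessions.

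**Method.** Power of a one-sample, one-sided t-test = P(T > t₀.₉₅,ₙ₋₁), where T is noncentral t with n−1 degrees of freedom and noncentrality 5.5·√n / SD.

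**1. The plan's own figure.** At n=30 and SD 10, noncentrality = 5.5 × √30 / 10 = 3.01 and the critical value is 1.70. Power is 90.3%, so the stated 90% reproduces. A two-sided test gives 82.9%, and reading 5.5% as relative (4.125 points) gives 71.3%; the one-sided, absolute reading is therefore the plan's.

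**2. The SD of a rate out of 8.** With equally attended sessions and within-person correlation ρ,

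SD = 100 × √[ p(1−p)/8 × (1+7ρ) ].

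- ρ = 0, p = 0.805: 100 × √(0.805 × 0.195 / 8) = 14.0 points.
- ρ = 0.1 (assumed, for illustration): 14.0 × √1.7 = 18.3 points.
- Solving for SD = 10: ρ = [(10/14.008)² − 1]/7 = −0.07. Attending one session would have to make attending another less likely.

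Strongly unequal session attendance can also lower the SD. With independent sessions, five attended by everyone and three by 48% give 100 × √(3 × 0.48 × 0.52)/8 = 10.8. A milder pattern, falling linearly from 95% to 66%, gives 13.6. Dropout raises it: if 5% stop at a point spread evenly over sessions 1 to 7 (assumed), with the overall mean held at 80.5%, the SD is 16.7.

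**3. Power for 80.5% against 75%.**

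| SD (points) | n=30 | n=40 | n=55 |
|---|---|---|---|
| 10 (as stated) | 90.3% | 96.2% | 99.1% |
| 14.0 (independent sessions) | 67.5% | 78.7% | 89.1% |
| 18.3 (ρ = 0.1, assumed) | 48.6% | 59.0% | 71.2% |

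The t-test formula is slightly generous for such discrete data. Simulating Binomial(8, 0.805) attendance (200,000 runs) gives 66.8%, 77.3% and 87.6% in the middle row, hence about 67/78/88–89%.

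**4. Excess over 75% detectable with 90% power.**

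| SD (points) | n=30 | n=40 | n=55 |
|---|---|---|---|
| 10 | 5.5 | 4.7 | 4.0 |
| 14.0 | 7.7 | 6.6 | 5.6 |
| 18.3 | 10.0 | 8.6 | 7.3 |

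The SD is held fixed along each row. Recomputing the independent-sessions SD at each detectable mean changes the middle row only to 7.4, 6.5 and 5.6. At SD 14.0, 90% power for 5.5 points needs 57 participants.

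**5. Where it stops mattering.** At a true mean of 85% with independent sessions, SD = 100 × √(0.85 × 0.15 / 8) = 12.6, and power for the 10-point excess is 99.5% at n=30.

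**The case against.** The strongest reply is that the plan concludes for 55, not 30. On one of the two readings of 5.1, 55 people attend at least one session. Independent sessions then give 88–89% power and a detectable excess of 5.6 points, close to the stated 90% and 5.5. This stands: a reader might infer that the study is underpowered at its planned size, and under independence with 55 attenders it is not. It does not cover the other reading, with about 40 attending, or a larger SD.

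Second, 6.0 and 6.2 describe an exploratory open pilot with descriptive analyses, and no go/no-go rule hangs on this power. That lowers the weight. It does not remove the point, since the plan itself chose a threshold, an alpha and a power.

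Third, the true SD is unknown. A reader might infer that it is 14; the documents do not say so. Independent attendance gives an SD of 10 at a mean near 91%, so the figure may have come from better-attended groups. What stands is that 10 is unexplained and fits poorly at 80.5%. All the figures here also treat participants as independent, although 5.5.2 has groups of about 6.

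Fourth, 6.8 lists means and attendance is collected, so a bound could be computed later. True; what is missing is a bound stated in advance.

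A reader might go further on the denominator. From "All patients, regardless of whether they are counted towards the 55 accrual goal, will be included in the feasibility assessment" one could argue that with 55 enrolled and 40 taking part, mean participation could not exceed 40/55 = 72.7%, below 75% even with perfect attendance. The text does not support this. The sentence introduces proportions eligible, ineligible, enrolled, refusing, lost, withdrawn and completing, not mean attendance. It also covers people found ineligible at the test call, who cannot sensibly enter an attendance mean. The fair criticism is only that the denominator is unstated.

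**Conclusion.** The point holds in a limited form. The 90% at n=30 is computed correctly from an SD that is unsourced and, for an 8-session count at 80.5%, would need negative within-person correlation or strongly unequal session attendance. With independent, equally attended sessions, power at n=30 is about 67%, some 23 points lower; at the roughly 40 expected to take part it is about 78%. At 55 attenders the claim nearly survives under independence but falls to 71% with an assumed within-person correlation of 0.1. These figures are conditional on the attendance model, and the consequence is confined to true participation modestly above 75%. The absence from 6.8 of any bound or test against 75% rests on no such assumption. Severity is minor to should-fix, given the exploratory pilot.

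**What to change.** 1. In 6.2, replace the single SD with a range, for example: *Participation is the number of sessions attended out of 8. With SDs of 10, 14 and 18.3 points (14 being the value for independent, equally attended sessions at a mean of 80.5%, and 18.3 assuming a within-person correlation of 0.1), the excess over 75% detectable with 90% power at one-sided 0.05 is 5.5, 7.7 and 10.0 points with 30 participants, 4.7, 6.6 and 8.6 with 40, and 4.0, 5.6 and 7.3 with 55.* Keep the figures for the chosen analysis n. If attendance data from the team's earlier 3RP groups (section 1.2) support a particular SD, cite them and use it instead.

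2. Reconcile 30, 40 and 55 across 5.1 and 6.2, and state which is the analysis n.

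3. In 6.8, Aim a, add: *Mean sessions attended out of 8 will be reported with a one-sided 95% lower confidence bound and compared with 75%.* State the denominator (those attending at least one session, or all enrolled). Keep the 6-of-8 completer proportion as a separate descriptive measure.

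The cost is wording in 5.1 and 6.2 and one or two sentences in 6.8. No extra participants or data are needed, because sessions per participant are already recorded. The downside is that the stated power becomes less favourable.
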